5.3 Subject Enrollment

Before subjects begin participation in any study-specific activities/procedures, Amgen requires a copy of the site's written institutional review board/independent ethics committee (IRB/IEC) approval of the protocol, informed consent form, and all other subject information and/or recruitment material, if applicable (see Section 11.3).

The subject must personally sign and date the IRB/IEC and Amgen approved informed consent before commencement of study-specific procedures. For Part 3c only: If a subject is younger than 20 years at the time of signing the informed consent, informed consent must be obtained both from the subject and his/her legal representative.

Each subject who enters into the screening period for the study receives a unique subject identification number before any study-related activities/procedures are performed. The subject identification number will be assigned manually **or automatically**. This number will be used to identify the subject throughout the clinical study and must be used on all study documentation related to that subject.

The unique study identification number will consist of 11 digits. The first 3 digits will represent the last 3 digits of the protocol number (eg, 161). The next 5 digits will

represent the country code and site number (eg, 66001) and will be identical for all subjects at the site. The next 3 digits will be assigned in sequential order as subjects are screened (eg, 001, 002, 003). For example, the first subject to enter screening at US site 66001 will receive the number 16166001001, and the second subject at the same site will be 16166001002. The subject identification number must remain constant throughout the entire clinical study; it must not be changed after initial assignment, including if a subject is rescreened.

All screening tests and procedures should be performed within 14 days of administration of the first dose of AMG 176 (day 1), or itraconazole (ie, day -17 to day -3) for Part 3d, unless otherwise indicated. Subjects may be re-screened up to 2 additional times at the discretion of the investigator. The subject must be re-consented if a re-screening attempt occurs outside of the 14-day screening period. Subjects who are deemed ineligible will be documented as screen failures (see Section [5.4](#)).

Subjects may be eligible to enroll once all screening tests and procedures are completed and results indicate that all eligibility criteria are met. A site representative will complete and send the subject registration form and/or enrollment eligibility worksheet to the sponsor or designee. The Amgen representative will acknowledge receipt and return confirmation of dose cohort (dose exploration part) or group (dose expansion part), respectively, to the site.

A subject is considered enrolled when the investigator decides that the subject has met all eligibility criteria. The investigator is to document this decision and date, in the subject's medical record and in/on the enrollment case report form (CRF).

The subject identification number must remain constant throughout the entire clinical study; it must not be changed after initial assignment, including if a subject is rescreened.

5.4 Screen Failures

Screen failures are defined as subjects who consent to participate in the clinical study but are not subsequently dosed with AMG 176. A minimal set of screen failure information will be collected that includes demography, screen failure details, eligibility criteria, and any serious adverse events.

Individuals who do not meet the criteria for participation in this study (screen failure) may be rescreened. Refer to Section [8.1.1](#).

6. Treatments

Study treatment is defined as any investigational product(s), non-investigational product(s), placebo, or medical device(s) intended to be administered to a study subject according to the study protocol.

Note that in several countries, investigational product and non-investigational product are referred to as investigational medicinal product and non-investigational medicinal product, respectively.

The Investigational Product Instruction Manual (IPIM), a document external to this protocol, contains detailed information regarding the storage, preparation, destruction, and administration of each treatment.

6.1 Treatment(s) Administered

The Amgen Investigational Product used in this study is AMG 176. The non-investigational products used in this study (azacitidine) may be considered investigational in some countries.

The Investigational Product Instruction Manual (IPIM), a document external to this protocol, contains detailed information regarding the storage, preparation, destruction, and administration of AMG 176.

6.1.1 Investigational Product: AMG 176

All investigational products will be administered at the research facility by a qualified staff member. A physician must be available at the time of administration of Investigational Product.

Description

AMG 176 is an anhydrous crystalline material that is a white to light brown powder, which is formulated as a sterile concentrate for solution for infusion. The solution is administered IV after dilution into an IV bag containing normal saline (0.9% sodium chloride).

Dosage Form

The AMG 176 investigational product is formulated as a sterile concentrate for solution for infusion at a concentration of 25 mg/mL in 10% w/w 2-hydroxypropyl beta-cyclodextrin, and buffered with 100 mM glycine to pH 9.0. AMG 176 is supplied as a sterile, preservative-free solution for IV infusion.

Drug Supply and Storage

AMG 176 will be supplied as either a 10 mL liquid deliverable volume in a single use (20R) glass vial or a 14.4 mL liquid deliverable volume in a single use (30R) glass vial.

The primary container closure system for the 10 mL presentation consists of a 20R borosilicate glass vial with a 20 mm elastomeric stopper, and an aluminum seal with flip-off dust cover. A single use vial containing 14.4 mL fill of 25 mg/mL AMG 176 has also been developed for use in the clinic. Additional details are provided in the IPIM.

It is recommended that AMG 176 be stored at or below 25°C, protected from light, and according to the storage and expiration information (where required) provided on the label that is affixed to the package containing the investigational product.

Dosage, Administration, and Schedule

AMG 176 will be administered on a 28-day cycle. The dosing schemes include BIW administration for 3 weeks of 4 in a cycle (6 doses per cycle, see below), QW administration every week of the cycle (4 doses per cycle, see below), or a conventional AML dosing scheme administering azacitidine in combination with AMG 176 (7 doses per cycle). Prior to dosing on day 1 of every cycle, body surface area (BSA) must be calculated. Each cycle of AMG 176 BIW is defined as an IV infusion once daily for 2 consecutive days followed by a 5-day break and repeated each week for 3 weeks (Part 1a, 3a, 4 [cohorts 5a and 5b]) followed by 1 week with no treatment. Intravenous BIW begins at study day 1. Each cycle of AMG 176 QW is defined as an IV infusion QW followed by a 6-day break and repeated each week either for 3 weeks followed by 1 week with no treatment (Part 1b), or for 4 consecutive weeks (Parts 3b, 3c, and 4 [cohorts 1-4]). Dosing begins at study day 1. Part 5 dosing will be based on MTCD determined in Part 4.

Ramp-up dosing will be utilized whenever the target dose level is at 180 mg/m² or higher to mitigate the risk of TLS. Ramp-up dosing consists of an initial dose at cycle 1 week 1 of 120 mg/m² followed by an increase to the target dose level for subsequent doses. Decisions regarding the AMG 176 ramp-up dosing period regimen, ramp-up period starting dose, dosing increments, will be made by DLRT and communicated to the IRB/IEC, as appropriate (see Section 11.3).

Tumor lysis syndrome prophylaxis must be initiated in all subjects prior to all ramp-up dosing of AMG 176 and prior to all subsequent dose escalations (ie, first dose on the targeted cohort dose level). Hospitalization and monitoring should begin the night before

AMG 176 administration and must continue until at least the 24-hour post-dose (QW schedule) or until 48 hours post the first dose in the BIW dosing schedule. Refer to Section 6.1.4.1 for additional details on prophylaxis and management of TLS.

The AMG 176 dose, start date/time, stop date/time and lot number is to be recorded for each subject in the electronic CRF (eCRF).

The AMG 176 infusion time will be 120 (\pm 5) minutes.

If a subject develops a reaction during or after the AMG 176 infusion, immediate treatment should be initiated according to best clinical practice. Increase monitoring of vital signs as medically indicated until the subject is deemed medically stable in the opinion of the investigator. All medication and symptoms should be documented in the eCRF.

Intra-subject Dose Escalation

For each part, DLTs will be assessed during the DLT evaluation period. Subjects who complete the DLT-observation period without experiencing a DLT may proceed to a higher dose level or different dosing schedule cohort once the target cohort has been deemed safe by the DLRT and after consultation with the sponsor. Dose-limiting toxicities experienced by subjects who proceeded to a higher dose or different schedule will not be considered for dose level decisions. However, the DLRT will take this information into account to inform dose escalation recommendations.

6.1.2 Non-investigational Products: Azacitidine and Itraconazole

In some countries, the non-investigational products used in this study (azacitidine and itraconazole) may be considered investigational based on regional requirements.

Refer to regional prescribing information for full details regarding azacitidine and itraconazole, respectively.

6.1.2.1 Azacitidine (Parts 4 and 5)

Description

Azacitidine is a pyrimidine nucleoside analog of cytidine. The empirical formula is C₈H₁₂N₄O₅. The molecular weight is 244 g/mol.

The mechanism of action is through hypomethylation of DNA and direct cytotoxicity. Hypomethylation may restore normal function to genes that are critical for differentiation and proliferation. The concentration of azacitidine required for maximum inhibition of DNA methylation in vitro does not cause major suppression of DNA synthesis.

Formulation

Azacitidine is a white to off-white solid. Azacitidine was found to be insoluble in acetone, ethanol, and methyl ethyl ketone; slightly soluble in ethanol/water (50/50), propylene glycol, and polyethylene glycol; sparingly soluble in water, water-saturated octanol, 5% dextrose in water, N-methyl-2-pyrrolidone, normal saline, and 5% Tween 80 in water; and soluble in dimethylsulfoxide (DMSO).

The finished product is supplied in a sterile form for reconstitution as a suspension for **SC** injection or reconstitution as a solution with further dilution for IV infusion.

Storage

Store unreconstituted vials at 25°C; excursions permitted to 15°C to 30°C (5°F to 86°F).

Accountability

Sites will be required to record and document subject compliance regarding azacitidine dosing. The quantity administered, route, start date/time, stop date/time, and lot number of azacitidine are to be recorded on each subject's CRF(s). Stop date/time is required to be recorded on each subject's CRF(s) only for IV administrations.

Azacitidine will not be supplied by Amgen for this study unless required by local regulation or in response to a regional supply shortage. In Japan, azacitidine will be supplied by Amgen for this study.

Packaging

Azacitidine is supplied as a lyophilized powder in 100 mg single use vials packaged in cartons of 1 or 2 vial(s). Vials contain 100 mg of azacitidine and 100 mg of mannitol as a sterile lyophilized powder.

Dosage, Administration, and Schedule

For Parts 4 and 5A, azacitidine will be administered at a dose of 75 mg/m² either IV or SC, as recommended in the prescribing information, daily for the first 7 days of a 28day cycle. The dose may be increased to 100 mg/m² if no beneficial effect is seen after 2 cycles and if no toxicity other than manageable nausea and vomiting has occurred.

For Part 5B, all subjects will receive 7 days of azacitidine IV or SC daily at 75 mg/m² on days 1 - 5, 8 - 9 of each 28-day cycle.

On days where azacitidine is co-administered with AMG 176, azacitidine will be given before AMG 176. A minimum of a 30-minute gap between the administration of azacitidine and AMG 176 is recommended.

6.1.2.2 Itraconazole (Part 3d)

Description

Itraconazole is a synthetic triazole antifungal agent. Itraconazole is a 1:1:1:1 racemic mixture of 4 diastereomers (2 enantiomeric pairs), each possessing 3 chiral centers.

Itraconazole has a molecular formula of $C_{35}H_{38}Cl_2N_8O_4$ and a molecular weight of 705.64.

The mechanism of action is through inhibition of the cytochrome P450-dependent synthesis of ergosterol, which is a vital component of fungal cell membranes.

Formulation

Itraconazole is a white to slightly yellowish powder. It is insoluble in water, very slightly soluble in alcohols, and freely soluble in dichloromethane. It has a pKa of 3.70 (based on extrapolation of values obtained from methanolic solutions) and a log (n-octanol/water) partition coefficient of 5.66 at pH 8.1.

Itraconazole capsules contain 100 mg of itraconazole coated on sugar spheres (composed of sucrose, maize starch, and purified water). Inactive ingredients are hard gelatin capsule, hypromellose, polyethylene glycol 20 000, titanium dioxide, FD&C Blue No. 1, FD&C Blue No. 2, D&C Red No. 22, and D&C Red No. 28.

Storage

Store at 15°C to 25°C. Protect from light and moisture.

Accountability

Oral itraconazole capsules should be taken with a full meal. Sites will be required to record and document subject compliance regarding itraconazole dosing.

Itraconazole will not be supplied by Amgen for this study unless required by local regulation.

Packaging

Itraconazole is supplied as a commercially available oral capsule containing 100 mg of itraconazole, with a blue opaque cap and pink transparent body. The capsules are supplied in unit-dose blister packs of 3 × 10 capsules, bottles of 30 capsules, and in the PulsePak® containing 7 blister packs × 4 capsules each.

Dosage, Administration, and Schedule

Subjects will receive oral itraconazole capsules (200 mg) QD starting at approximately 8 am on day -3 through day 4 (total of 7 days) to achieve adequate CYP3A4 inhibition prior to, and following, AMG 176 administration.

6.1.3 Medical Devices

There are no investigational devices in this study.

Other non-investigational medical devices may be used in the conduct of this study as part of standard care.

Non-investigational medical devices (eg, syringes, sterile needles), that are commercially available are not usually provided or reimbursed by Amgen (except, for example, if required by local regulation). The investigator will be responsible for obtaining supplies of these devices.

6.1.4 Other Protocol-required Therapies

All other protocol-required therapies including, allopurinol, that are commercially available are not provided or reimbursed by Amgen (except if required by local regulation). The investigator will be responsible for obtaining supplies of these protocol-required therapies.

6.1.4.1 Tumor Lysis Prophylaxis (All Subjects)

There is a potential for TLS in subjects affected by hematologic malignancies especially in those with bulky disease, elevated pretreatment lactate dehydrogenase (LDH) levels, elevated leukocyte count, renal dysfunction, and dehydration. To mitigate the risk of TLS, AMG 176 ramp-up dosing (see Section 6.1.1) will be used and TLS prophylaxis must be initiated in all subjects prior to all ramp-up dosing of AMG 176 and prior to all subsequent dose escalations (ie, first dose on the targeted cohort dose level). In Part 5B, subjects will receive ramp-up dosing on days 1 and 2 of week 1 in cycle 1 followed by the target dose starting on day 3. Prior to administering these doses, all electrolyte values (including potassium, uric acid, phosphorous, calcium, and creatinine) should be reviewed and must be within normal range. However, LDH is not mandatory.

All subjects will be hospitalized to monitor for TLS and all TLS monitoring assessments will be performed as outlined in the Schedule of Assessments (see Section 1.3).

The management recommendations below focus on the minimum initial responses required. If a diagnosis of TLS is established, ongoing intensive monitoring and

multi-disciplinary management will be conducted per institutional protocols (Coiffier et al, 2008; Cairo et al, 2004).

Tumor lysis syndrome prophylaxis includes:

- Allopurinol or equivalent should be used to reduce uric acid level. This should be initiated at least 72 hours prior to dosing. Treatment may need to be continued for up to 5 weeks. Other agents to reduce uric acid level, such as rasburicase, may be used per principal investigator discretion and the institutional guidelines. Dosing per institutional guidelines.
- NOTE: Allopurinol is unapproved for TLS prophylaxis in Japan.
- Hospitalization and monitoring, should begin the night before AMG 176 administration and must continue until at least 24 hours post-dose (QW schedule) or until 48 hours post the first dose in the BIW dosing schedule
- NOTE: Subjects in Part 3c will be hospitalized for a minimum of 29 days beginning from the night before AMG 176 administration in the first cycle.
- IV hydration must be started the night before AMG 176 administration and to be continued until at least 24 hours post-dose (QW schedule) during hospitalization as clinically tolerated (refer to Section 11.8.1 for more details about the level of IV hydration required)
- Monitoring of electrolyte values is required prior to dosing anytime a dose is higher than one previously given to the subject. This will include at the following times:
 - Prior to the week 1, day 1 dose
 - Prior to each dose during the ramp-up period
 - Prior to the initial dosing at the target dose level
- Prior to administering these doses, all electrolyte values (including LDH, potassium, uric acid, phosphorus, calcium and creatinine) must be reviewed and within normal range (samples must be drawn within 24 hours prior to dosing of AMG 176). The investigator's decision to proceed with AMG 176 treatment initiation will be based on these laboratory values.

Within the first 24 hours after either the first dose or dose escalation, if any laboratory criteria for TLS are met, no additional AMG 176 doses should be administered until resolution. A rapidly rising serum potassium is a medical emergency.

Prophylactic dose reductions for potassium, phosphorus and/or uric acid values at the high end of normal range should be considered.

If the potassium, uric acid, inorganic phosphate and/or creatinine values are higher than the normal range or the calcium is lower or higher than the normal range, this (these) value(s) can be approved following a discussion between the Amgen medical monitor and investigator.

On the AMG 176 dosing days chemistry labs must be performed pre-dose (within 4 hours before AMG 176 administration), 2, 4, 8, 12 and 24 hours after the start of AMG 176 infusion. Pre-dose labs will be used as baseline to assess potential

electrolytes abnormalities occurring post AMG 176 administration. These labs must be reviewed in real time by the investigator.

Day 2 dosing of AMG 176 (BIW schedule) should not be administered until the 24 hours post dose laboratory values are reviewed by the investigator.

All 24-hour laboratory assessments may be taken \pm 2 hours, if necessary.

Monitor for signs and symptoms of TLS (eg, fever, chills, tachycardia, nausea, vomiting, diarrhea, diaphoresis, hypotension, muscle aches, weakness, paresthesias, mental status changes, confusion, and seizures). If any clinical features are observed, recheck potassium, phosphorus, uric acid, calcium and creatinine within 1 hour.

Additional information on the management recommendations of laboratory abnormalities can be found in Section [11.2](#).

- Nephrology (or acute dialysis service) consultation should be considered on admission (based on investigator discretion) for hospitalized subjects per institutional guidelines to ensure emergency dialysis is available and the appropriate staff is aware and prepared.

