Upon completion of Part 4, enrollment will commence in Part 5A to confirm the safety and tolerability of the two selected doses along with the dosing schedule (QW or BIW) and to further evaluate the preliminary efficacy of AMG 176 in combination with azacitidine. In Part 5A, approximately 48 subjects will be enrolled, with 24 subjects randomized to the cohort of AMG 176 120 mg/m² in combination with azacitidine and 24 subjects randomized to the cohort of AMG 176 240 mg/m² in combination with azacitidine, where the same dosing schedule (QW or BIW) will be used for both cohorts. Simon's two-stage minimax design (Simon, 1989) will be used for conducting the trial in each cohort of Part 5A. Details about Simon's two-stage minimax design are provided in Section 9.4.1.1.

In Part 5B, 20 subjects will be enrolled to test 2 regimens. The enrollment of Part 5B will start after Part 5A is complete. Regimen 1 consists of administering AMG 176 at 240 mg/m² QD for 3 days + 4 days off followed by BIW dosing on weeks 2 and 3. If this schedule is deemed safe by the DLRT after 6 subjects have enrolled on Regimen 1 cohort, the next 6 subjects in Regimen 2 cohort will receive AMG 176 at 240 mg/m² QD for 5 consecutive days, and then BIW on week 2. Safety data will be monitored continually.

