4.3 Justification for Investigational Product Dose

AMG 176 is administered as an IV infusion once daily twice weekly (BIW) followed by 5 days break in Part 1a, Part 3a, and cohorts 5a and 5b of Part 4. AMG 176 is administered as an IV infusion for one day followed by 6 days break (QW); in Part 1b, 3b, 3c, 3d, and 4 (cohorts 1-4). This schedule was repeated for a total of 3 consecutive weeks followed by 1 week off in the earlier parts of the study, which are now closed to enrollment (ie, Parts 1a, 1b, and 3a). AMG 176 was administered QW in Part 3c, which is now closed to enrollment, for a total of 4 consecutive weeks. AMG 176 was administered QW in Parts 3b, 3d, and 4 (cohorts 1-4) for a total of 4 consecutive weeks and BIW in Part 4 (cohorts 5a and 5b) for the first 3 weeks of each 28-day cycle. Additionally, AMG 176 will be administered in Part 5 either QW for a total of 4 consecutive weeks or BIW for the first 3 weeks of each 28-day cycle. This 28-day duration is considered 1 cycle. Ramp-up dosing of 120 mg/m² will be utilized whenever the target dose level is at 180 mg/m² or higher, applicable to all indications (AML or MM) and all dosing schedules (BIW or QW) to mitigate the risk of TLS (see Section 4.1).

The AMG 176 doses proposed in this study are:

Multiple Myeloma

- For MM Part 1a BIW potential dose levels are: 30, 40, 50, 60, 120, 180, 240, 360, and 480 mg/m² of AMG 176 (IV; BIW).
- For MM Part 1b QW potential dose levels are: 180, 240, 360, and 480 mg/m² of AMG 176 (IV; QW). The starting dose level will be 180 mg/m² tested with BIW dosing in MM subjects but dosing will be only one day per week instead of day 1 and day 2.

Acute Myeloid Leukemia

- For AML Part 3a of the study, potential dose levels are: 60, 120, and 180 mg/m² of AMG 176 (IV; BIW). The starting dose level will be the latest dose tested in MM subjects and cleared as safe and tolerable by the DLRT up to a maximum starting dose of 60 mg/m². Part 3a doses will be given once daily twice weekly (BIW) followed by a 5-day break and repeated each week for 3 weeks followed by 1 week with no treatment.
- For AML Part 3b, potential dose levels are: 120, 180, and 240 mg/m² of AMG 176 (IV; QW). For AML Part 3c, the potential dose level is 120 mg/m² (IV; QW). For AML Part 3d, the dose selected is 60 mg/m² (IV; QW).

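### The protocol gives one ramp-up dose in one place and two in another for week 1 of cycle 1 in Part 5B, and states no follow-up period before Regimen 2 may open

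*Protocol*

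**What the plan says.** **Regimen descriptions.** Protocol Section 4.1.1 sets a dose of 240 mg/m² for Regimen 1, given "QD for 3 days + 4 days off followed by BIW dosing on weeks 2 and 3". The synopsis and Table 4-1 say the same, and give Regimen 2 as 240 mg/m² daily for 5 days followed by two doses in week 2. None of these descriptions mentions ramp-up.

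**General ramp-up rule.** Section 6.1.1 says: "Ramp-up dosing will be utilized whenever the target dose level is at 180 mg/m² or higher to mitigate the risk of TLS". It defines ramp-up as "an initial dose at cycle 1 week 1 of 120 mg/m² followed by an increase to the target dose level for subsequent doses". Table 4-1 footnote a repeats this rule and is attached to the dose-level column, which includes Part 5B. The AMG 176 dosing note in Table 1-9 also refers to a ramp-up dose in the singular. It then describes Part 5B dosing without any ramp-up.

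**Part 5B in the tumor lysis section.** Section 6.1.4.1 says: "In Part 5B, subjects will receive ramp-up dosing on days 1 and 2 of week 1 in cycle 1". It places the first target dose on day 3. The sentence gives no dose for days 1 and 2; the section refers back to Section 6.1.1 for ramp-up dosing.

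**Scope.** Section 4.3 calls the ramp-up "applicable to all indications (AML or MM) and all dosing schedules (BIW or QW" and does not name the conventional schedule. Figure 1-9 (Part 5A) has a ramp-up footnote; the footnotes to Figure 1-10 (Part 5B) have none.

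**Opening Regimen 2.** Section 4.1.1 lets Regimen 2 start once six subjects are enrolled on Regimen 1 and the DLRT judges that schedule safe. No cycle or length of follow-up is attached to that judgement.

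**The concern.** A site that follows Section 6.1.1 gives the target dose on day 2. A site that follows Section 6.1.4.1 gives it on day 3. Both would be following the protocol. Three things depend on which is meant.

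- **Tumor lysis safety.** Section 2.3.2.1 reports a fatal case of tumor lysis syndrome. Section 6.1.4.1 requires electrolytes to be reviewed before the first dose, before each ramp-up dose and before the first target dose, so those days move with the reading. Section 6.2.1.2.1 attributes a tumor lysis DLT to the ramp-up period if it arises there, so an event on day 2 could be classified either way. This last effect carries less weight in Part 5B, because within Parts 4 and 5 DLTs are an endpoint in Part 4 only.
- **What has been observed when Regimen 2 opens.** If ramp-up applies at all, cycle 1 does not deliver the stated week 1 schedule.
- **Exposure reporting.** SAP Section 5 divides actual cumulative dose by the planned per-protocol dose. Relative dose intensity is reported under SAP Section 9.6.8 and is not among the analyses dropped in SAP Section 10. The SAP carries the 240 mg/m² regimens and the general ramp-up footnote, but not the two-day version.

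**Working it through.** **Inputs.** Target 240 mg/m² (Sections 1.1 and 4.1.1, Table 4-1). Ramp-up dose 120 mg/m² (Section 6.1.1). Regimen 1 has 3 doses in week 1 and 2 in each of weeks 2 and 3. Regimen 2 has 5 doses in week 1 and 2 in week 2. Assumption: each ramp-up day in Section 6.1.4.1 uses 120 mg/m².

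**The plan's own figure.** Section 6.1.1 gives 7 doses per cycle for the conventional schedule. Regimen 1: 3 + 2 + 2 = 7. Regimen 2: 5 + 2 = 7. Both agree. The nominal cycle total is 7 × 240 = 1680 mg/m².

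**Cycle 1 with k ramp-up doses.** With n doses in week 1:

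- week 1 total = 120k + 240(n − k)
- cycle 1 total = 1680 − 120k

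| Regimen | k | Week 1 doses (mg/m²) | Week 1 total | % of nominal | Doses at 240 in week 1 | Cycle 1 total | % of nominal |
|---|---|---|---|---|---|---|---|
| 1 | 0 | 240, 240, 240 | 720 | 100 | 3 | 1680 | 100 |
| 1 | 1 | 120, 240, 240 | 600 | 83.3 | 2 | 1560 | 92.9 |
| 1 | 2 | 120, 120, 240 | 480 | 66.7 | 1 | 1440 | 85.7 |
| 2 | 0 | 240 on 5 days | 1200 | 100 | 5 | 1680 | 100 |
| 2 | 1 | 120, then 240 on 4 days | 1080 | 90.0 | 4 | 1560 | 92.9 |
| 2 | 2 | 120, 120, then 240 on 3 days | 960 | 80.0 | 3 | 1440 | 85.7 |

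**First target dose.** Day 2 with k = 1 and day 3 with k = 2. It would be day 1 if no ramp-up applied.

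**Consecutive target doses.** With k = 1 or 2, no Regimen 1 subject receives 240 mg/m² on three consecutive days in cycle 1, and no Regimen 2 subject receives it on five. Ramp-up is confined to cycle 1, so the stated pattern can first occur in cycle 2.

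**Relative dose intensity, cycle 1.** A subject given exactly two ramp-up doses and no other reduction scores 1440/1680 = 85.7% if planned dose is nominal, 1440/1560 = 92.3% if it allows one ramp-up dose, and 1440/1440 = 100% if it allows two. These ratios are in mg/m² and carry over to mg at a constant body surface area. Later cycles at full dose dilute the difference.

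**The case against.** **A specific rule normally overrides a general one.** Section 6.1.4.1 names Part 5B and the days, and the general definition was written with the weekly and twice-weekly schedules in mind. The protocol foresees ramp-up of more than one dose: Section 6.1.4.1 refers to checks before each dose of the ramp-up period, and Table 1-9 allows for additional step-doses. Section 6.1.1 also leaves the ramp-up regimen to the DLRT. This makes an intended Part 5B exception plausible. But neither Section 6.1.1 nor Table 4-1 footnote a carries that exception, and the DLRT's power to change ramp-up does not settle what the protocol now instructs.

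**A reader might infer three rival schedules.** That is too strong. Under footnote a, 240 mg/m² reads most naturally as the target. Part 4 Cohort 5b is written the same way, with its ramp-up in a footnote to Figure 1-8. The no-ramp-up reading rests only on the scope wording in Section 4.3 and the missing note in Figure 1-10. These leave the matter unclear but do not amount to a third instruction.

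**A reader might infer that cycle 1, with a 28-day window, decides whether Regimen 2 opens.** The documents do not say so. The decision is a DLRT judgement after six subjects have enrolled, and Appendix 3 has the DLRT review data beyond the initial DLT period as well. What stands is that no follow-up period is stated.

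**A reader might infer that the stated schedule may never be tested.** That holds for cycle 1 only. A ramped first cycle is also the study-wide design for targets of 180 mg/m² or higher, so it is not in itself a fault of Part 5B.

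**The week 1 percentages look larger than the effect.** One and two ramp-up doses differ by 120 mg/m², once per subject. This is fair, and the cycle 1 totals are shown for that reason.

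**Conclusion.** The contradiction is real: one ramp-up dose and two cannot both apply to Part 5B. One versus two changes the cycle 1 total by 120 mg/m² in either regimen. Two ramp-up doses give 67% (Regimen 1) and 80% (Regimen 2) of the nominal week 1 dose, and 86% of nominal over cycle 1 in both. The practical weight lies in the day of the first target dose and the tumor lysis checks tied to it, and secondly in the planned dose for relative dose intensity.

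Under either ramp-up version, the DLRT could open Regimen 2 before any subject has received the stated Regimen 1 week, because no follow-up time is required. Whether that would happen depends on accrual and DLRT practice, which the documents do not settle.

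The totals assume 120 mg/m² on each ramp-up day. SAP Section 10 says the study was terminated early, and the documents do not say whether Part 5B enrolled anyone. If it did, the planned dose still has to be settled for reporting.

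**What to change.** - Reconcile the following to one Part 5B cycle 1 schedule: the synopsis table, Table 4-1 and its footnote a, Section 4.1.1, Section 4.3, Section 6.1.1, Section 6.1.4.1, the Table 1-9 dosing note and the Figure 1-10 footnotes. If Section 6.1.4.1 is meant as an exception for Part 5B, say so in Section 6.1.1 and give the dose for each ramp-up day.
- Use that schedule as the planned cumulative dose for Part 5B in SAP Section 5.
- State what data, including which cycle or cycles and how much follow-up, the DLRT decision on Regimen 2 rests on.

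The choice of schedule belongs to the sponsor and the DLRT, and no dose is proposed here. The cost is protocol wording and one line in the SAP. If Part 5B enrolled no one, the clarification is needed only for the record.
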